#### **9.4.10 Treatment Compliance**

The Investigator is responsible for ensuring that dosing is administered in compliance with the protocol. Delegation of this task must be clearly documented and approved by the Investigator.

All infusions of study medication will be administered at the clinic under the supervision of clinic staff. Infusion volumes, and start and stop times of the infusions will be recorded in the eCRF.

An inventory of the study medication supplies will be performed by the site or authorized study designee and recorded onto the Drug Accountability Log in the subject's source document records or equivalent.

## **9.5 Efficacy, Quality-of-Life, Pharmacokinetic, and Safety Variables**

The Schedule of Assessments was previously provided in [Section 2.1](#).

### **9.5.1 Efficacy Variables**

Efficacy assessments will be performed for both eyes at each assessment time point. The "study eye" (i.e., most severely affected eye) will remain the same as that identified at the Baseline (Day 1) Visit of Study HZNP-TEP-301. Both eyes will be assessed for efficacy but the study eye will be used to assess the primary outcome measure.

Efficacy will be assessed by proptosis (measured as exophthalmos evaluation of the Clinical Measures of Severity using a Hertel instrument provided by the Sponsor for consistency in measurement), CAS (7-item scale), diplopia (measured as part of the Clinical Measures of Severity) and Clinical Measures of Severity (including motility restriction assessments).

#### **9.5.1.1 Proptosis (Exophthalmos)**

Proptosis assessments will be performed using a Hertel exophthalmometer provided by the Sponsor for consistency in measurement, and (except when strictly unavoidable) the same Hertel instrument and same observer should be used at each evaluation for the full duration of the study. Additionally, the same intercanthal distance (ICD) must be used on each occasion. Instructions for the measurement of proptosis are included in [Section 17.2](#).

Proptosis will be measured for each eye on Day 1 and Weeks 6, 12, 18, and 24 (or premature withdrawal [PW]) during the Treatment Period, and at Months 7, 9, and 12 (or PW) during the Follow-Up Period. Measurements will be recorded on the Clinical Measures of Severity eCRF under exophthalmos.

#### **9.5.1.2 Clinical Activity Score (CAS)**

The CAS will be completed on Day 1 and Weeks 6, 12, 18, and 24 (or PW) during the Treatment Period, and at Months 7, 9, and 12 (or PW) during the Follow-Up Period using the 7-item European Group on Graves' Ophthalmopathy (EUGOGO) amended CAS [Mourits et al, 1989] ([Table 9.2](#)).

**Table 9.2 Clinical Activity Score (CAS) Assessment**

Item 	Description
1.	Spontaneous orbital pain.
2.	Gaze evoked orbital pain.
3.	Eyelid swelling that is considered to be due to active (inflammatory phase) TED/GO.
4.	Eyelid erythema.
5.	Conjunctival redness that is considered to be due to active (inflammatory phase) TED/GO (ignore “equivocal” redness).
6.	Chemosis.
7.	Inflammation of caruncle or plica.

 Each item is scored (1=present; 0=absent) and scores for each item are summed for total score.

To promote consistency in data collection across clinical trial sites, all Investigators will be provided with training and copies of the Clinical Manifestations chapter in *Graves' Orbitopathy: A Multidisciplinary Approach – Questions and Answers* [Dickinson, 2010]. Except when strictly unavoidable, the same observer should conduct each CAS evaluation for the full duration of the study.

#### **9.5.1.3 Clinical Measures of Severity**

Based on the EUGOGO Consensus Statement [Bartalena et al, 2008; Wiersinga et al, 2006], the following items will be assessed on Day 1 and Weeks 6, 12, 18, and 24 (or PW) during the Treatment Period, and at Months 7, 9, and 12 (or PW) during the Follow-Up Period ([Table 9.3](#)). Except when strictly unavoidable, the same observer should conduct each evaluation of severity measure for the full duration of the study.

**Table 9.3 Clinical Measures of Severity**

Item and Assessment Scale	Minimum change required for classifying overall response
Exophthalmos (measured in mm using the same Hertel exophthalmometer provided by the Sponsor for consistency in measurement and same intercanthal distance for each individual patient)	Decrease $\geq$ 2 mm
Lid aperture (distance between the lid margins in mm with the patient looking in the primary position, sitting relaxed and with distant fixation)	Decrease $\geq$ 2 mm
Swelling of the eyelids (absent, mild, moderate, severe)	Decrease $\geq$ One grade
Redness of the eyelids (absent, present)	Decrease $\geq$ One grade
Redness of the conjunctiva (absent, present)	Decrease $\geq$ One grade
Conjunctival edema (absent, present)	Decrease $\geq$ One grade
Inflammation of the caruncle or plica (absent, present)	Decrease $\geq$ One grade
Subjective diplopia score  0=no diplopia; 1=intermittent (diplopia in primary position of gaze, when tired or when first awakening); 2=inconstant (diplopia at extremes of gaze); 3=constant (continuous diplopia in primary or reading position)	Decrease $\geq$ One grade
Eye muscle involvement (ductions in degrees)	Increase $\geq 8^\circ$ in at least one direction of gaze
Corneal involvement (absent/punctate keratopathy/ulcer)	Decrease $\geq$ One grade
Optic nerve involvement Best corrected visual acuity Color vision Optic disc Relative afferent pupillary defect (APD) (absent/present) Visual fields if optic nerve compression is suspected.	Change of best corrected visual acuity by $\geq$ 2 lines on Snellen chart, or substantial color vision change, or significant change of visual fields, or significant change in optic disc appearance, or (Dis-) appearance of relative afferent pupillary defect

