#### 9.5.1.3.1 Motility Restriction – Details for Measurement

Motility is examiner assessed by estimating the degrees of restriction in eye movements. It will be assessed at the same time points as the Clinical Measures of Severity.

Monocular excursions in horizontal and vertical directions of gaze are recorded using the light reflex (LR) test [Dolman et al, 2012].

The clinician will shine a pen light in line with the eye being examined in ambient room light and observe the subject's eye along the light's axis. The subject will be asked to look in the 4 cardinal directions and the position of the light reflex is viewed on the surface of the cornea. If the light touches the limbus, the eye is assessed to be turned 45 degrees, if half way between the limbus and pupil edge, the eye is assessed at 30 degrees, and if it is at the pupil edge, it was

assessed at 15 degrees. Intermediate ductions are judged by estimating the light position between these points to the nearest 5 degrees.

The monocular ductions of each eye (degrees) will be recorded for adduction, abduction, supraduction and infraduction.

Except when strictly unavoidable, the same observer should conduct each duction evaluation for the full duration of the study.

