8.3.2.1. Categorical Response Variables

[Table 2](#) provides a list of each Clinical Measures of Severity item and the assessment scale for classifying overall response.

Table 2: Clinical Measures of Severity

Clinical Measures of Severity Item and Assessment Scale	Minimum change required for classifying overall response
Exophthalmos (measured in mm using the same Hertel exophthalmometer and same intercanthal distance for each individual subject)	Decrease \geq 2 mm
Lid aperture (distance between the lid margins in mm with the subject looking in the primary position, sitting relaxed and with distant fixation)	Decrease \geq 2 mm
Swelling of the eyelids (absent, mild, moderate, severe)	Decrease \geq One grade
Redness of the eyelids (absent, present)	Decrease \geq One grade
Redness of the conjunctiva (absent, present)	Decrease \geq One grade
Conjunctival edema (absent, present)	Decrease \geq One grade
Inflammation of the caruncle or plica (absent, present)	Decrease \geq One grade
Subjective diplopia score (0=no diplopia; 1=intermittent, i.e. diplopia in primary position of gaze, when tired or when first awakening; 2=inconstant, i.e. diplopia at extremes of gaze; 3=constant, i.e. continuous diplopia in primary or reading position)	Decrease \geq One grade
Eye muscle involvement (ductions in degrees)	Increase \geq 8° in at least one direction of gaze
Corneal involvement (absent/punctate keratopathy/ulcer)	Decrease \geq One grade

Clinical Measures of Severity Item and Assessment Scale	Minimum change required for classifying overall response
Optic nerve involvement (best corrected visual acuity, color vision, optic disc, relative afferent pupillary defect (absent, present), and visual fields if optic nerve compression is suspected).	Change of best corrected visual acuity by ≥ 2 lines on Snellen chart, or substantial color vision change, or significant change of visual fields, or significant change in optic disc appearance, or (Dis-) appearance of relative afferent pupillary defect

Response is assessed individually for each item.

Subjects who have a Study Baseline assessment on a particular measure for which improvement is not possible (i.e. they have the best possible assessment) will be considered to be a responder if they maintain the Study Baseline assessment. The analysis of optic nerve involvement will be generated only if at least 10% of the subjects have optic nerve decompression.

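### On the 5-degree duction scale, an eye one step (40 degrees) below the top value can never be an eye-muscle responder, even if it normalises, while an eye at 45 degrees throughout is one (minor)

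*Protocol*

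**What the plan says.** - **Response rule.** For eye muscle involvement, Protocol Table 9.3 requires a rise of at least 8 degrees "in at least one direction of gaze". The table in SAP 8.3.2.1 lists the same item, "Eye muscle involvement (ductions in degrees"), with the same threshold.
- **Measurement scale.** Protocol 9.5.1.3.1, repeated in SAP 8.3.2.2, sets three anchors for the light reflex: 15, 30 and 45 degrees. For the highest: "If the light touches the limbus, the eye is assessed to be turned 45 degrees". Between anchors: "Intermediate ductions are judged by estimating the light position between these points to the nearest 5 degrees". No value above 45 is defined.
- **Directions.** "The monocular ductions of each eye (degrees) will be recorded for adduction, abduction, supraduction and infraduction".
- **Best-value rule.** SAP 8.3.2.1 makes an exception for a baseline "for which improvement is not possible (i.e. they have the best possible assessment"). A person who starts there counts as a success by holding that value. Table 9.3 has no such rule. Protocol 9.6 gives the SAP precedence.
- **Use.** The percentage of responders on each severity item is the second exploratory endpoint (Protocol 9.6.1.3, SAP 4.3). Mean change in motility is a separate exploratory endpoint, summarised for each direction under SAP 8.3.2.2.

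**The concern.** The threshold and the scale do not fit together near the top. At a worst duction of 40, improvement is possible but a gain of 8 degrees is not. The SAP's exception covers only baselines already at the best value, and neither document covers a baseline one step below it.

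The resulting scores contradict each other. Two eyes can be identical and fully normal at Week 24, yet the one that improved is a failure and the one that did not change is a success. For this item the responder percentage would then depend partly on how many eyes began at 40 rather than at 45. The table is shown by lead-in treatment, so a difference between columns could partly reflect that baseline mix.

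**Working it through.** The plan states no figure on this point, so there is none to reproduce. The check is an enumeration of the scale.

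**Inputs.** Threshold 8 degrees (Table 9.3, SAP 8.3.2.1); step 5 degrees, top anchor 45 degrees and four directions per eye (Protocol 9.5.1.3.1, SAP 8.3.2.2). The best-value rule is applied to the whole item: the best possible assessment means all four ductions at 45.

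**Step 1: gains that can be recorded.** Both readings are multiples of 5, so gains are 0, 5, 10 and so on. The smallest that satisfies the rule is 10.

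**Step 2: largest possible gain.** From a baseline duction b it is 45 − b. For b = 40 this is 5, which is below 8. For b = 35 it is 10, which meets the rule. An eye is therefore unable to respond when every duction is 40 or 45 and at least one is 40.

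**Step 3: count the patterns.** Baselines with every direction at 40 or 45: 2⁴ = 16. One of these is all 45 and falls under the best-value rule. The other 16 − 1 = 15 cannot respond. The full grid has ten values (0 to 45) in four directions, or 10⁴ = 10,000 patterns, so these are 15 of 10,000 possible patterns. That is a count of patterns, not of subjects.

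**Step 4: score examples under the written rules.**

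| Baseline | Week 24 | Largest gain | Score |
|---|---|---|---|
| 40/45/45/45 | 45/45/45/45 | 5 | Non-responder |
| 40/40/40/40 | 45/45/45/45 | 5 | Non-responder |
| 35/45/45/45 | 45/45/45/45 | 10 | Responder |
| 45/45/45/45 | 45/45/45/45 | 0 | Responder (best-value rule) |

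**Step 5: sensitivity to the ceiling.** With the highest value set at 40, 50 or 55 instead of 45, the count of restricted patterns that cannot respond is still 15. The trap always sits exactly one step below whatever the top value is.

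**The case against.** The strongest case against is about reach, and most of it stands.

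- **Narrow scope.** A reader might infer that any mildly restricted eye that normalises is scored a failure. The documents do not define mild restriction, and an eye whose worst duction goes from 35 to 45 responds. Only the one-step deficit is caught.
- **Unknown frequency.** Neither document says how many subjects have a worst duction of 40 at baseline. The effect on the reported percentage could be nil.
- **Inferred maximum.** Neither document calls 45 the maximum or the normal value. The one-step result holds for any ceiling on this grid, but the score for the never-restricted eye needs some best possible value to exist.
- **Motility change is reported elsewhere.** A reader might infer that the motility results as a whole are unsound. SAP 8.3.2.2 summarises observed values and change from Study Baseline for all four ductions in both eyes, so a recovery from 40 to 45 is visible there. No primary or secondary endpoint uses the responder rule for this item.
- **Other readings of the rule.** It is tempting to say that the threshold must be rewritten as 10, or that a gain in one direction should not count when another worsens. The first changes no classification on a 5-degree grid. The second is a preference for another definition: the plan deliberately states a single-direction criterion.

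One defence does not succeed. Reading the best-value rule loosely, as covering any baseline from which response is impossible, conflicts with the SAP's own gloss, which limits it to the best possible assessment. A duction of 40 is not that when 45 can be recorded.

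**Conclusion.** The point holds in a narrow form and is minor. Eyes with no baseline duction below 40 and at least one at 40 are non-responders on this item whatever happens, including full normalisation, while eyes at 45 throughout are responders. The conclusion follows from the recording grid, the threshold and the SAP's best-value rule taken together. It assumes only that 45 is the best recordable value in each direction.

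Its reach is one item of an exploratory, descriptive endpoint. The shift in the responder percentage cannot be computed without the baseline distribution of ductions. The documents do not support a claim that the motility analysis as a whole is wrong, or that the 8-degree threshold misclassifies eyes with larger deficits.

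**What to change.** In SAP 8.3.2.1, extend the best-value rule for eye muscle involvement: an eye with all four ductions at the best possible value (45 degrees) at the visit is a responder, whether it maintained or reached that value. State there that 45 is taken as the best possible value. All 15 trapped baselines can then respond by normalising, and the two identical Week 24 eyes receive the same score. The 8-degree wording can stay.

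The work is a sentence of SAP text and a small programming change on data already collected. The real cost is that some one-step changes due to reading error will count as response. The documents give no reading error, but the cost can be bounded for an eye truly at 45/45/45/40 throughout. Assume independent, symmetric errors of equal size in each direction, and let p be the chance that an error is at least +2.5 degrees. The 40 is then recorded as 45 with probability p, and each true 45 is recorded as 45 with probability 1 − p. The chance of recording all 45 is p(1 − p)³, which peaks at p = 1/4 with 27/256, or 10.5%. Chance responses added by the fix for such an eye cannot exceed that, whatever the error SD. If this is judged too many, the alternative is to keep the rule and footnote the table with the number of eyes whose worst baseline duction was 40.

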#### 9.5.1.3.1 Motility Restriction – Details for Measurement

Motility is examiner assessed by estimating the degrees of restriction in eye movements. It will be assessed at the same time points as the Clinical Measures of Severity.

Monocular excursions in horizontal and vertical directions of gaze are recorded using the light reflex (LR) test [Dolman et al, 2012].

The clinician will shine a pen light in line with the eye being examined in ambient room light and observe the subject's eye along the light's axis. The subject will be asked to look in the 4 cardinal directions and the position of the light reflex is viewed on the surface of the cornea. If the light touches the limbus, the eye is assessed to be turned 45 degrees, if half way between the limbus and pupil edge, the eye is assessed at 30 degrees, and if it is at the pupil edge, it was

assessed at 15 degrees. Intermediate ductions are judged by estimating the light position between these points to the nearest 5 degrees.

The monocular ductions of each eye (degrees) will be recorded for adduction, abduction, supraduction and infraduction.

Except when strictly unavoidable, the same observer should conduct each duction evaluation for the full duration of the study.

### **9.5.2 Quality-of-Life Assessment**

The GO-QoL questionnaire [C. B. Terwee et al, 1998] will be completed on Day 1 and Weeks 6, 12, and 24 (or PW) during the Treatment Period, and at Months 7 and 12 (or PW) during the Follow-Up Period.

The GO-QoL is a 16-item self-administered questionnaire divided into 2 subsets and used to assess the perceived effects of TED by the subjects on (i) their daily physical activity as it relates to visual function, and (ii) psychosocial functioning. The English version of the questionnaire is included in [Section 17.3](#).

### **9.5.3 Pharmacokinetic Measurements**

Blood samples will be collected in 5 mL serum separator tube (SST) collection tubes to evaluate PK at the following time points: pre- and post-infusion on Day 1 and Weeks 3 and 9 of the Treatment Period; single samples will also be collected at Weeks 1, 4, and 24 (but not PW) of the Treatment Period. Samples will be collected, processed, and stored at  $\geq -70^{\circ}\text{C}$  at the site until shipment to the central laboratory. [REDACTED] will store the samples at  $\geq -70^{\circ}\text{C}$  until shipment to [REDACTED] for PK testing (see [Table 6.1](#)).

Instructions for processing, handling, storing and shipping of PK samples will be detailed in a laboratory manual that will be provided to each site prior to site initiation. A central laboratory will be used for PK sample analysis.

### **9.5.4 Safety Variables**

Safety will be assessed via AE and concomitant medication use monitoring, immunogenicity testing, physical and ophthalmic examinations, vital signs, clinical safety laboratory evaluations (complete blood count, chemistry [including thyroid panel and HbA1c], and urinalysis), pregnancy testing (if applicable), and ECGs. The study will also be monitored by a DSMB.

#### **9.5.4.1 Adverse Events**

##### **9.5.4.1.1 Definitions**

###### **9.5.4.1.1.1 Adverse Event Definition**

According to ICH, an AE is any untoward medical occurrence in a subject or clinical investigation subject administered a pharmaceutical product and which does not necessarily have a causal relationship with this treatment. An AE can therefore be any unfavorable and unintended sign (including an abnormal laboratory finding), symptom, or disease temporally

associated with the use of a medicinal (investigational) product, whether or not considered related to the medicinal (investigational) product.

Pre-existing conditions that worsen during a study are to be reported as AEs. New findings reported from the on-study ophthalmic examinations will not be reported as AEs if according to the Investigator the abnormalities are related to TED and not considered related to the investigational product.

Unchanged, chronic conditions are **NOT** considered AEs and should not be recorded on the AE pages of the eCRF unless there is a clear exacerbation of a chronic condition.

Disease progression can be considered as a worsening of a subject's condition attributable to the disease for which the study drug is being studied (i.e., TED). It may be an increase in the severity of the disease under study and/or increases in the symptoms of the disease. The development of worsening proptosis may be considered as disease progression and not an AE. Events, which are unequivocally due to disease progression, should only be reported as AEs if they fulfill any of the SAE criteria or are the reason for discontinuation of treatment with the study drug.

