#### **9.5.4.1.1.2 Serious Adverse Event Definition**

A TEAE, baseline event, or suspected adverse reaction is considered serious if, in the view of either the Investigator or Sponsor, it results in any of the following outcomes:

- Death. This includes any death that occurs during the conduct of a clinical study, including deaths that appear to be completely unrelated to the study drug (e.g., car accidents).
- Life-threatening adverse experience. An AE or suspected adverse reaction is considered life-threatening if, in the view of either the Investigator or the Sponsor, its occurrence places the subject at immediate risk of death. It does not include an AE or suspected adverse reaction that, had it occurred in a more severe form, might have caused death.
- Persistent or significant disability or incapacity.
- Inpatient hospitalization or prolongation of an existing hospitalization.
- Congenital anomaly or birth defect.
- Other medically important event which, according to appropriate medical judgment, may require medical or surgical intervention to prevent one of the outcomes listed above.

Surgical procedures or other therapeutic interventions themselves are not AEs, but the condition for which the surgery/intervention is required is an AE and should be documented accordingly.

Elective surgeries that require hospitalization and treatment received at an emergency room or similar facility will not be considered as SAEs unless one of the definitions of an SAE listed above is met.

In addition, hospitalizations for planned procedures are not considered an AE unless they are prolonged hospitalizations, and emergency room visits less than 24 hours in duration are not considered hospitalizations.

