#### **9.5.4.4 Physical and Ophthalmic Examinations, Height, and Weight**

A physical examination, including complete undilated ophthalmic examination, will be performed at Baseline (Day 1) and thereafter at Weeks 1, 6, 12, 18, and 24 (or PW) during the Treatment Period and Month 12 (or PW) of the Follow-Up Period.

The ophthalmic exam should include best-corrected visual acuity, pupil exam, color vision assessment, Ishihara color plates (or equivalent) or related red desaturation, intraocular pressure and slit lamp exam. If significant abnormalities are noted compared with previous visits, including a loss of 2 lines or more of vision, development of pupil abnormalities including afferent pupillary defect (APD), rise in intraocular pressure, development of corneal infiltrates or other abnormalities not here specified but of concern to the ophthalmologist, further investigations of visual function will be conducted according to the ophthalmologist decision.

New findings reported from on-study ophthalmic examinations will not be reported as AEs if, according to the Investigator, the abnormalities are related to TED and not related to the study drug.

Physical exam will include assessment of presence or absence of pretibial myxedema on Day 1 and Week 24 (or PW) of the Treatment Period and Month 12/PW of the Follow-Up Period. If present, measurements of instep and calf will be taken.

Weight will be measured at Baseline and every 12 weeks throughout the study (Weeks 12 and 24 [or PW] during the Treatment Period and Months 9 and 12 [or PW] of the Follow-Up Period). The dose on Day 1 may be based on the weight determined at the most recent clinic visit, provided the most recent visit was within the prior 3 weeks. The doses on Week 3 through Week 9 will be based on the weight determined on Day 1. The weight used in the Week 12 dose calculation can be the weight determined on Day 1 or the weight obtained at Week 12. The weight obtained at Week 12 can be used to adjust the dose beginning at Week 12 or Week 15 through Week 21, as appropriate.

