10.6. OPTHALMIC EXAMINATION

A complete undilated ophthalmic examination will be performed as part of the physical examination. The ophthalmic exam should include best-corrected visual acuity, pupil exam, color vision assessment, Ishihara color plates (or equivalent) or related red desaturation, intraocular pressure and slit lamp exam. If significant abnormalities are noted compared with previous visits, including a loss of 2 lines or more of vision, development of pupil abnormalities including APD, rise in intraocular pressure, development of corneal infiltrates or other abnormalities not here specified but of concern to the ophthalmologist, further investigations of visual function will be conducted according to the ophthalmologist decision.

New findings reported from on-study ophthalmic examinations will not be reported as AEs if according to the investigator the abnormalities are related to TED and not related to the study drug.

For each of the assessments (pupil exam, color vision assessment, intraocular pressure, and slit lamp exam), shift tables will be presented providing the count of subjects with each type of finding (normal, abnormal - not clinically significant [NCS], or abnormal - clinically significant [CS]) at Study Baseline compared to each post-baseline visit by treatment received in HZNP-TEP-301 with percentages based on subjects with a non-missing value at the Study Baseline and post-baseline visit. In addition, a summary table will be provided for loss of 2 lines or more of vision (yes or no) including the count and percent of subjects at each post-baseline visit.

Similar summaries will be provided comparing to the HZN-001 Baseline.

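### The AE exemption for TED-related eye-examination findings has no explicit exception for serious or treatment-stopping findings, and it conflicts with the disease-progression rule in the same section

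*Protocol*

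**What the plan says.** Protocol 9.5.4.1.1.1 contains two rules that can apply to the same event.

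- **Exemption.** "New findings reported from the on-study ophthalmic examinations will not be reported as AEs if according to the Investigator" two conditions are met: "the abnormalities are related to TED and not considered related to the investigational product". Seriousness and discontinuation are not mentioned.
- **Progression rule.** The last paragraph defines disease progression as worsening attributable to TED. The scope of its reporting rule is "Events, which are unequivocally due to disease progression". For events within that scope, the section says that they "should only be reported as AEs if they fulfill any of the SAE criteria or are the reason for discontinuation of treatment".

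The exemption appears twice more. Protocol 9.5.4.4, which describes the ophthalmic examination itself, has "New findings reported from on-study ophthalmic examinations will not be reported as AEs if, according to the Investigator", and SAP 10.6 has "New findings reported from on-study ophthalmic examinations will not be reported as AEs if according to the investigator". Both give the same two conditions. Neither carries the seriousness and discontinuation clause or refers back to the progression rule.

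Three other protocol statements bear on the question:

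- 9.5.4.1.1.1, immediately before the exemption: "Pre-existing conditions that worsen during a study are to be reported as AEs".
- 9.5.4.1.1.2: "A TEAE, baseline event, or suspected adverse reaction is considered serious if" one of the listed outcomes results. The same section adds that a condition needing surgery or another intervention is itself an AE.
- 9.5.4.1.5: every SAE from consent to 30 days after discharge goes to the sponsor within 24 hours, regardless of relationship to study drug.

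**The concern.** Protocol 7.1.1 names corneal ulceration and dysthyroid optic neuropathy among the sight-threatening conditions of moderate-to-severe TED. The study examination (acuity, pupils, color vision, intraocular pressure, slit lamp) is well suited to finding them. If such a finding is attributed to TED and meets an SAE criterion, one sentence of 9.5.4.1.1.1 says it is not an AE and another says it is.

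Two investigators could therefore treat the same event differently, each with protocol text in support. If the exemption is followed, the event may not reach the 24-hour SAE report. It would also be absent from the serious-TEAE table and the table of TEAEs leading to permanent withdrawal, both of which SAP 10.3 builds from recorded AEs. All subjects receive teprotumumab and there is no concurrent control, so the split between TED and drug rests on the investigator's judgement.

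**Working it through.** No arithmetic applies, and the documents state no figure on this point. The check is to take one event through each rule. The event is a new corneal ulcer, first seen at a scheduled examination, judged related to TED and not to study drug, and meeting an SAE criterion.

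| Rule | Result for this event |
|---|---|
| Exemption (Protocol 9.5.4.1.1.1 and 9.5.4.4; restated in SAP 10.6) | Not reported as an AE |
| Progression rule (Protocol 9.5.4.1.1.1, last paragraph) | Reported, if unequivocally due to progression |
| Worsening pre-existing condition (Protocol 9.5.4.1.1.1) | Reported, if the ulcer is seen as worsening of existing TED and not as a new finding |
| Surgery or intervention (Protocol 9.5.4.1.1.2) | The condition is an AE, if intervention is required |
| SAE reporting (Protocol 9.5.4.1.5) | Reported within 24 hours, if it counts as an SAE |

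The answers conflict, and no sentence gives one rule precedence.

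**Does the SAE definition settle it?** Not clearly. 9.5.4.1.1.2 applies seriousness to a TEAE, a baseline event or a suspected reaction. An exempted finding is not recorded as an AE, so it is not plainly a TEAE. It is new, so it is not a baseline event. It has been judged unrelated to study drug, so it is not a suspected reaction. The 24-hour rule in 9.5.4.1.5 covers SAEs, so it helps only once the event has passed that definition.

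**Do the thresholds fit together?** They run against each other. The exemption needs only a relation to TED, while the progression rule needs an unequivocal link to progression. Read literally, a serious event with certain attribution is reported and one with weaker attribution to TED is exempt.

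**How often can the conflict arise?** Post-baseline ophthalmic examinations are at Weeks 1, 6, 12, 18 and 24, which is 5 visits for subjects who relapsed in the lead-in study. Month 12 is added for lead-in proptosis non-responders, giving 5 + 1 = 6. These are opportunities and not expected events.

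**What is captured even if the exemption is followed?**

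- SAP 10.6: shift tables (normal, abnormal not clinically significant, abnormal clinically significant) for pupils, color vision, intraocular pressure and slit lamp, plus a count of subjects losing 2 or more lines.
- Protocol 9.5.1.3 and Table 9.3: corneal involvement, with ulcer as a category, and optic nerve involvement. Post-baseline these are assessed at Weeks 6, 12, 18 and 24, and for lead-in non-responders also at Months 7, 9 and 12.
- SAP Table 14.2.7.1 summarises these measures as responder counts. The optic nerve analysis is produced only if the 10% condition in SAP 8.3.2.1 is met. Listing 16.2.6.2.4.3 shows corneal and optic nerve data for all subjects and has no such condition.
- SAP 7.1: discontinuations tabulated by reason. Protocol 9.3.3 allows worsening eye disease to be recorded under lack of efficacy.

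None of these outputs flags seriousness, and none triggers an expedited report.

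**The case against.** The strongest reply is that the exception is already in the section. Progression is defined as worsening attributable to TED, and a new TED-related ulcer or optic neuropathy fits that definition. The two sentences can then be read together: routine TED findings at examination are not AEs, and serious or treatment-stopping ones are. The rules on worsening conditions, on conditions needing intervention, and on reporting SAEs regardless of relatedness all point the same way. In addition, the exemption does not cover a finding considered related to study drug, the eye data are collected and displayed elsewhere, and the SAP sentence does not instruct sites, who report under the protocol.

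Much of this stands. The combined reading is sensible and may be what was intended. It means that loss from SAE reporting is only a risk, and the listed outputs mean that the finding itself does not vanish. The operative conflict is in the protocol, and the SAP merely restates one side of it.

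The reply does not remove the ambiguity. The combined reading has to be supplied by the reader. Section 9.5.4.4, which governs the examination, gives the exemption alone. The opening of the SAE definition leaves an exempted finding without a clear route in.

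**Conclusion.** The point holds as a conflict between stated reporting rules. The exemption lacks an explicit seriousness or discontinuation exception, the progression rule in the same section has one, and the documents do not say which governs. A serious TED-attributed finding first seen at a study examination can be handled in opposite ways across sites, and may be absent from expedited SAE reports and from the AE and SAE tables.

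The size cannot be computed. The number of such events is unknown and probably small, but any one of them would bear on the safety result of an uncontrolled study. This makes it a change that should be made at low cost, and not a threat to the efficacy analysis.

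A reader might infer more: that such an event can never be an SAE, that it disappears from every table, or that the worst eye outcomes are the ones most likely to be missing. The documents do not support this. Other text in Protocol 9.5.4.1.1.1, 9.5.4.1.1.2 and 9.5.4.1.5 can be read to require reporting. The findings remain in the ophthalmic and severity outputs without a seriousness flag, and no figure indicates which outcomes would be lost.

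The conclusion assumes that sites apply the written text and have no further reporting instruction outside these two documents.

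**What to change.** Reconcile the passages by adding the section's own exception to the exemption in Protocol 9.5.4.1.1.1 and 9.5.4.4, and mirror it in SAP 10.6 so that the analysis document matches. Suggested clause: *unless the finding meets any SAE criterion or is the reason for discontinuing study drug, in which case it is reported as an AE/SAE.*

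The cost is one clause in three places. It reuses a standard the protocol already states and changes no treatment, visit or assessment. The downside is possibly a few more reported AEs or SAEs. If the sponsor already intends these events to be reported, the edit only makes that explicit.
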